### Specific Ethical Issues

None

## 15 FINANCING AND INSURANCE

University College London holds insurance against claims from participants for injury caused by their participation in the trial. Participants may be able to claim compensation if they can prove that UCL has been negligent. However, as this trial is being carried out in a hospital, the hospital continues to have a duty of care to the participant of the trial. University College London does not accept liability for any breach in the hospital's duty of care, or any negligence on the part of hospital employees. This applies whether the hospital is an NHS Trust or otherwise.

Participants may also be able to claim compensation for injury caused by participation in this trial without the need to prove negligence on the part of University College London or another party. Participants who sustain injury and wish to make a claim for compensation should do so in writing in the first instance to the Chief Investigator, who will pass the claim to the Sponsor's Insurers, via the Sponsor's office.

The NIHR Research for Patient Benefit, Jon Moulton Charitable Foundation Trust and St. Peters Trust fund this trial.

## 16 REPORTING AND DISSEMINATION

Results of scientific interest from the trial and any parallel translational work will be submitted for consideration for presentation to professional and scientific meetings, and publications in peer reviewed professional and scientific literature. They may also be included in theses and dissertations.

Any submissions are to have authorisation from the chief investigator and co-investigators upon review by the TMG. Authorship will be determined on a per paper basis. The chief investigator will have final say if agreement cannot be reached.

### 16.1 Patient and Public Involvement

Patient feedback on the design of the trial was obtained. The PPI events were supported by Macmillan Cancer (Charity no 261017) and Orchid (Charity no 1080540). Participants, patients and their families were asked specifically about the level of blinding, the burden of follow-up appointments and priorities in their recovery from RALP.

Following their feedback, NeuroSAFE PROOF now informs men following surgery of their NS status, though blinding to allocation status (intervention or control) is maintained. Patient representatives sit on both the trial steering committee (TSC) and the Data Monitoring Committee (iDMC) contributing to the oversight of the management of the trial. The trial is also funded by National Institute for Healthcare Research for Patient Benefit (NIHR RfPB) stream, which has patient members on their decision panels.

### 16.2 NeuroSAFE PhD report

NeuroSAFE PROOF will constitute a substantial part of the PhD research degree for [name]. [name] is enrolled at University College London within the Division of Surgery and Interventional Sciences. His supervisors are [name], [name] and [name] (Chief Investigator of NeuroSAFE PROOF). [name] anticipates finishing his PhD and submitting his thesis in July 2021. [name] has been heavily involved in the design and execution of the both the feasibility and the full-scale NeuroSAFE PROOF trial. Particularly, [name] has been influential in the establishment of the NeuroSAFE PROOF feasibility trial, day-to-day running of the trial, designing the full-scale NeuroSAFE PROOF trial, writing protocol versions 2-5, writing and submitting the protocol manuscripts for peer review and publication, co-ordinating PPI on behalf of the NeuroSAFE PROOF team, selecting the primary endpoint, standardisation of reporting of crucial elements of the trial methodologies (such as the role of MRI reporting, the surgical response to the positive NeuroSAFE, statistical handling of the NS status of surgery, and health economics analysis). [name] will write his thesis on evaluation of extra-prostatic extension and surgical margin status in men undergoing RARP. This work will rely heavily upon the skills and techniques developed as part of his role in NeuroSAFE

PROOF. Given that the NeuroSAFE PROOF trial will form a significant part of [name] thesis, it is intended that [name] be given confidential, unblinded access to data and results of statistical analyses. This will mean that the thesis will be made open access after an embargo period (determined by the CI), to enable first publication of the trial results in a journal.

4.9	Descriptive outcomes analysis.....	21
4.9.1	Positive Surgical Margins	21
4.9.2	Time to erectile function recovery.....	21
4.9.3	Time to urinary continence.....	21
4.9.4	Oncological outcome	22
4.10	Subgroup analysis	22
4.10.1	Rationale for the subgroup analysis.....	22
4.10.2	Interaction test.....	22
4.10.3	Subgroup analysis within the non-BNSR participants.....	22
4.11	Missing data sensitivity analysis	23
4.11.1	Missing at random	23
4.11.2	Missing not at random	23
5	References	24
6	Appendix	25
6.1	IIEF-5 scoring	25
6.2	IIEF-6 scoring	26
6.3	ICIQ scoring	27
6.4	Gleason score and Gleason grade group	27
6.5	Cambridge prognostic groups.....	28

1 Trial summary

NeuroSAFE is a single blinded, IDEAL stage 3, multi-centre, randomised controlled trial to assess NeuroSAFE Robotic assisted radical prostatectomy (RARP) vs standard RARP in patients with prostate cancer. Patients will be randomised 1:1 to NeuroSAFE RARP (intervention group) vs Standard RARP (control group). This trial aligns with an IDEAL framework Stage 3 Assessment for the evaluation of complex surgical interventions.

1.1 *Summary table*

Scientific Title	A single blinded, IDEAL stage 3, multi-centre, randomized controlled trial to assess NeuroSAFE Robotic assisted radical prostatectomy (RARP) vs standard RARPs in men with prostate cancer
Short Title	NeuroSAFE at prostatectomy to optimize oncological and functional outcome. (NeuroSAFE PROOF)
Trial registration	NCT03317990
Aim	This is a fully powered RCT to assess the differences in functional and oncological outcomes between RARP using the NeuroSAFE intraoperative frozen section technique to navigate safe nerve sparing and standard UK practice RARPs
Countries of Recruitment	UK
Health Condition(s) or Problem(s) Studied	Robotic assisted radical prostatectomy for prostate cancer
Intervention	
Control group - standard RARP: Nerve-sparing strategy during RARP guided by routinely available pre-operative and intra-operative patient/disease information; mpMRI, biopsy tumour histology, DRE.
 
Intervention group – NeuroSAFE RARP: Nerve-sparing strategy during RARP guided by the NeuroSAFE technique during RARP.

Inclusion criteria	
 - Men opting to undergo RARP for organ confined prostate cancer (including radiological t3a). - Potent men (IIEF score of 22-25 on the first 5 questions of the IIEF-15 without any erectile function medical assistance) - Men who are continent of urine (no self-reported urinary incontinence) - Has given written informed consent - Ability to read English sufficiently to answer questionnaires and understand PIS

Exclusion criteria	
 - Unable to undergo RARP - Known overactive bladder - Any previous treatment for prostate cancer - Previous/current hormone treatment for prostate cancer - Nerve sparing deemed futile due to locally advanced disease by surgeon and radiologist
Number of sites	5
Study setting	Secondary care
Date of First Enrolment	10.10.18
Target Sample Size	Patient recruitment target in protocol: 404 patients Loss of follow-up: 10%
Primary Outcome	
 - IIEF-5 score at 12 months
Secondary Outcomes	
 - ICIQ at 3 months - ICIQ at 6 months - IIEF-6 at 12 months
Descriptive outcomes	
 - Time to erectile function recovery - Time to continence recovery - Positive surgical margins - Oncological outcomes at 12 months

1.2 *Objectives*

[figure not shown]
1.2.1 Primary objective

To assess the difference in erectile function between patients undergoing standard RARP (control group) and NeuroSAFE RARP (intervention group) at 12 months following treatment.

1.2.2 Secondary objectives

1. To assess the differences in urinary continence between patients undergoing standard RARP and NeuroSAFE RARP in the early period following treatment (3 and 6 months).
2. To report the oncological outcomes between patients undergoing standard RARP vs. NeuroSAFE RARP at 12 months.
3. To evaluate differences in overall quality of life outcomes between patients undergoing standard RARP vs NeuroSAFE RARP. (Not covered in this SAP)
4. Economic analysis to assess health resource use between standard RARP vs NeuroSAFE RARP at 12 months and up to 2 years post treatment. (Not covered in this SAP).

1.3 Trial diagram

1.4 Sample size

The sample size was based on detecting a 14% difference in the proportion of patients with an IIEF-5 score of 21 or above between the intervention (NeuroSAFE RARP) and control (standard RARP) groups (42% vs. 28%). 364 evaluable participants are required to have 80% power to detect such difference, with a two-sided alpha of 5%. Allowing for 10% drop out, the trial aimed to recruit 404 participants (202 per arm).

1.5 Randomisation

Block randomisation, stratified by site with 1:1 allocation. Randomisation was performed using the online based service Sealed Envelope™.

2 SAP introduction

2.1 Purpose of statistical analysis plan

This Statistical Analysis Plan (SAP) reports the details of the main effectiveness analyses of the NeuroSAFE randomised controlled trial.

Its purpose is to reduce bias in the analysis and presentation of study results by pre-specification of the analyses conducted and the statistical methods used, with an appropriate level of detail.

This SAP does not prevent adjustments to the statistical methodology during data analysis, provided that these adjustments are limited and justified. It also does not prevent conducting further secondary analyses that appear relevant after conducting the pre-specified analyses, these will also be limited, justified, and clearly identified.

This SAP covers only the main effectiveness (clinical) analysis of the trial up to the visit 4 follow-up (12 months). Longer term outcomes, quality of life and health economic evaluation will be covered in separate analysis plans.

2.3 Unblinding and data analysis

This SAP will be approved by BL and GS and published on a publicly available repository (such as figshare.com or ClinicalTrials.gov registry) before unblinding and final analysis.

Unblinding of data and analyses will commence after the last patient has completed the 12-month follow-up, all relevant data has been entered, data checks have been performed and the final analysis plan has been confirmed and approved. Majority of the analytical programs will be prepared prior to unblinding, including at least the primary outcome analysis.

A copy of the dataset at the time of the unblinding will be archived.

2.4 Data checking

Check will be conducted before the analysis to identify missing or implausible data. These checks include:

- Missing data
- Data outside expected range
- Inconsistency between dates, e.g. baseline data recorded after visit2.

Where abnormalities are identified, the data will be double-checked with the Clinical Trial Manager, who will liaise with the study sites who will enter the data directly to the study database

3 Data collection and outcomes definition

3.1 Schedule of assessments

Visit	Screening/ Baseline	Random- isation	Treatment	Visit 2 3 months	Visit 3 6 months	Visit 4 12 months
Informed consent	x					
Randomisation		x				
Fitness for surgery assessment	x					
PSA	x			x	x	x
Standard care referral pathway to regional uro-oncology centre	x					
MRI guided pre-op surgical planning			x			
RARP (standard/control or NeuroSAFE/intervention)			x			
Adverse events			x	x		
EQ-5D-5L – (in clinic)	x			x	x	x
ICIQ – (in clinic)	x			x	x	x
IIEF – (in clinic)	x			x	x	x
RAND36 – (in clinic)	x			x	x	x
Additional Erectile function questionnaire				x	x	x
Adjuvant Treatments Assessment				x	x	x
Health Resource Diaries data collection				x	x	x

The study collected additional data through electronic PROMs, paper PROMs or telephone consultation at 2 years (RAND36, IIEF, EQ-5D-5L, ICIQ and Additional EF questionnaire), and at 3, 4 and 5 years via additional medical record review (EPIC-26, PSA & Adjuvant therapies) and telephone or clinic (BCR rates). These longer-term data are not covered in this SAP.

3.2 Outcomes list

Primary outcome:

- IIEF-5 (the simplified International Index of Erectile Function) at 12 months.

Secondary outcomes:

- ICIQ (International Consultation on Incontinence Questionnaire) at 3 months *
- ICIQ at 6 months
- IIEF-6 at 12 months

* Main secondary outcome of interest is ICIQ at 3 months.

Descriptive outcomes:

- Erectile function recovery at 3, 6 and 12 months (binary and categorical)
- Time to erectile function recovery
- Continence recovery at 3, 6 and 12 months (binary)
- Time to urinary continence
- Oncological outcome at 12 months
- Positive Surgical Margins

Additional descriptive data will also include baseline characteristics, surgery and histopathology information, and serious adverse events, as described below.

3.3 Time points and dates

Data were aimed to be collected at baseline, 3 months after surgery (visit2), 6 months after surgery (visit3) and 12 months after surgery (visit4).

Outcomes were not always collected at the exact time point, particularly during the COVID-19 pandemic, and we allow some flexibility around the due date to determine if data could contribute to the analysis. Assessments were considered valid if they were collected within the following time windows:

- Visit 2 (3months): Recorded as visit 2, and conducted between 1 to 6 months after surgery
- Visit 3 (6 months): Recorded as visit 3, and conducted between 4 to 12 months after surgery
- Visit 4 (12-months): Recorded as visit 4, and conducted between 9 to 18 months after surgery

Date of PSA measurement available could vary more, and no specific window was applied. All available PSA data were used to determine the oncological outcome to maximally capture any cases of oncological failure.

Handling of missing visit dates:

If the questionnaire date was missing (for IIEF and ICIQ), we will look at the corresponding date for the other questionnaires. If the date of the other questionnaires were also missing, we will impute the date assuming the observation was recorded at the expected time point from surgery.

If the PSA date was missing, we will assume the observation was recorded at the expected time point from surgery.

Treatment date was recorded as day, month, year. If the day was missing, we will assume it was done on the 15th of the month. If the month or full date was missing, we will assume treatment has started on the expected visit date, checking this is consistent with the PSA and other information available.

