## 7.4 Table of Assessments

Visit	Screening/ Baseline	Randomisation	Treatment Visit 1	Visit 2 3 months ( $\pm 6$ weeks)	Visit 3 6 months ( $\pm 6$ weeks)	Visit 4 12 months ( $\pm 6$ weeks)	Visit 5  2 years ( $\pm 6$ weeks)	Visit 6 3 years ( $\pm 6$ weeks)	Visit 7 4 years ( $\pm 6$ weeks)	Visit 8 5 years ( $\pm 6$ weeks)	After Visit 8**
Informed consent	x										
Randomisation		x									
Fitness for surgery assessment	x										
PSA	x			x	x	x	x	x	x	x	x
Standard care referral pathway to regional uro-oncology centre	x										
MRI guided pre-op surgical planning			x								
RARP (standard/control or NeuroSAFE/intervention)			x								
Adverse events	x	x	x	x	x	x	x				
EQ-5D-5L – (P/C/E/T)*	x			x	x	x					
ICIQ – (P/C/E/T)*	x			x	x	x					
IIEF-5 – (P/C/E/T*)	x			x	x	x					
RAND36 – (P/C/E/T)*	x			x	x	x					
Additional Erectile Function (EF) questionnaire (P/C/E/T)*				x	x	x					
Additional Treatments Assessment				x	x	x	x	x	x	x	x
Health Resource Diaries data collection				x	x	x	x				
RAND36, IIEF, EQ-5D-5L, ICIQ and Additional EF questionnaire – (P/E/C/T)							x				
EPIC-26 questionnaire (P/E)*								x	x	x	x

\*P – Postal, E – Email, C – Clinic, T - telephone

\*\* after visit 8 data to be collected for a maximum frequency of annually

 Visits after 12 months dependent on future funding

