3.6 Descriptive outcomes definition

3.6.1 Erectile function recovery

Erectile function recovery (binary outcome) will be defined at each time-point, based on whether the IIEF-5 score is larger or equal to 15.

We will also report at each time-point the IIEF-5 as a categorical variable, as suggested in Rosen 1999: Severe (1-7), moderate (8-11), mild-moderate (12-16), mild (17-21), and no ED (22-25).

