3.6.2 Time to erectile function recovery

This will be defined as the time from surgery to the time of first reaching an IIEF-5 score larger or equal to 15.

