4.11.2 Missing not at random

We will also conduct a sensitivity analysis under not-at-random assumption using reference-based multiple imputation (Carpenter, 2013). We will impute the missing data under the 'last-mean-carried-forward' approach, corresponding to assuming the IIEF-5 score would have remained similar to the last score observed before dropping out (akin to the 'Last-Observation-Carried-Forward' approach, but appropriately allowing for other predictors, and variation in the imputed values).

The multiple imputation model will include the outcomes at each time point, the baseline covariates and other important predictors of missing data and will be stratified by arm. We will assume interim missing (missing assessments with later outcome data available) to be missing-at-random. If some participants have no IIEF-data available (at visit 2, 3 and 4), we will assume they had the lowest score at 3 months (1 for IIEF-5) at visit 2, before conducting the imputation.

The analysis model will be the same as the primary analysis model, and the results will be combined using Rubin's rules.

5 References

Avery, K. a. (2004). ICIQ: a brief and robust measure for evaluating the symptoms and impact of urinary incontinence. *Neurourology and Urodynamics: Official Journal of the International Continence Society*, 322--330.

Cappelleri, J. a. (2005). The Sexual Health Inventory for Men (SHIM): a 5-year review of research and clinical experience. *International journal of impotence research*, 307--319.

Cappelleri, J. C. (1999). Diagnostic evaluation of the erectile function domain of the International Index of Erectile Function. *Urology*, 346--351.

Carpenter, J. R. (2013). Analysis of longitudinal trials with protocol deviation: a framework for relevant, accessible assumptions, and inference via multiple imputation. *Journal of biopharmaceutical statistics*, 1352--1371.

Dinneen, E. a.-H.-P. (2022). Negative mpMRI rules out extra-prostatic extension in prostate cancer before robot-assisted radical prostatectomy. *Diagnostics*, 1057.

Dinneen, E. a.-M.-H. (2022). NeuroSAFE PROOF: study protocol for a single-blinded, IDEAL stage 3, multi-centre, randomised controlled trial of NeuroSAFE robotic-assisted radical prostatectomy versus standard robotic-assisted radical prostatectomy in men with localized prostate cancer. *Trials*, 584.

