6.1 IIEF-5 scoring

The primary outcome for this project is the simplified International Index of Erectile Function (IIEF-5).

The IIEF score, derived from the 15-item International Index of Erectile Function (IIEF), provides a concise evaluation tool for diagnosing erectile dysfunction (ED) and assessing its severity. Rosen selected these five specific items based on their ability to discern the presence or absence of erectile dysfunction, aligning with the NIH definition of the condition (Rosen, 1999). These items primarily centre on erectile function and satisfaction with intercourse.

The questionnaire used-was based the British Association of Urological Surgeons (BAUS) version of the IIEF questionnaire, which varies slightly from the original Rosen wording by allowing for a "0- Did not attempt intercourse" response for questions 2, 4, 5 and 7, as described in the table below:

NEUROSAFE PROOF STUDY QUESTIONNAIRE		ROSEN 1999
Q2	Over the past 3 months when you had erections with sexual stimulation, how often were your erections hard enough for penetration? 0 No sexual activity 1 Almost never or never 2 A few times (less than half the time) 3 Sometimes (about half the time) 4 Most times (more than half the time) 5 Almost always or always	Q2 When you had erections with sexual stimulation, how often were your erections hard enough for penetration? 1 Almost never /never 2 A few times (much less than half the time) 3 Sometimes (about half the time) 4 Most times (much more than half the time) 5 Almost always /always
Q4	Over the past 3 months during sexual intercourse, how often were you able to maintain your erection after you had penetrated (entered) your partner? 0 Did not attempt intercourse 1 Almost never or never 2 A few times (less than half the time) 3 Sometimes (about half the time) 4 Most times (more than half the time) 5 Almost always or always	Q3 During sexual intercourse, how often were you able to maintain your erection after you had penetrated (entered) your partner? 1 Almost never / never 2 A few times (much less than half the time) 3 Sometimes (about half the time) 4 Most times (much more than half the time) 5 Almost always / always
Q5	Over the past 3 months during sexual intercourse, how difficult was it to	Q4 During sexual intercourse, how difficult was it to maintain your erection to completion of intercourse?

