6.2 IIEF-6 scoring

IIEF-6 was scored similarly to the IIEF-5. It was based on summing the score to the questions 1, 2, 3, 4, 5 and 15 from the IIEF-15. Q2, Q4 and Q5 are shown in the IIEF-6 table below, and Q1 and Q15 are shown below.

Question 5 was scored as described above, before summing all the item, giving a total score between 1 and 30.

NEUROSAFE QUESTIONNAIRE

Q1	Over the past 3 months how often were you able to get an erection during sexual activity? 0 No sexual activity
-----------	-------------------------------------------------------------------------------------------------------------------

- 1 Almost never/never
- 2 A few times (much less than half the time)
- 3 Sometimes (about half the time)
- 4 Most times (much more than half the time)
- 5 Almost always/always

Q15 Over the past 3 months how do you rate your confidence that you could get and keep an erection?

- 1 Very low
- 2 Low
- 3 Moderate
- 4 High
- 5 Very high

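### Visit 2 erectile function forms count from 1 month after surgery but ask about the preceding 3 months, so early recovery in the descriptive outcomes may partly reflect preoperative function

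*SAP*

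**What the plan says.** SAP 3.3 gives the 3-month visit this acceptance rule: "Recorded as visit 2, and conducted between 1 to 6 months after surgery". The protocol's Table of Assessments (7.4) is narrower, at 3 months plus or minus 6 weeks, so its earliest form falls at about 6 weeks.

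SAP Appendix 6.1 gives the study wording of item 2: "Over the past 3 months when you had erections with sexual stimulation, how often were your erections hard enough for penetration". Items 4, 5 and 7 carry the same recall period. So does item 15 in Appendix 6.2: "Over the past 3 months how do you rate your confidence that you could get and keep an erection". These five items make up the IIEF-5. The answering instructions in Protocol 7.2.1 cover oral medication and erectile aids. They do not ask men to confine their answers to the time since surgery.

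The SAP summary table (1.1) sets the entry criterion: "Potent men (IIEF score of 22-25 on the first 5 questions of the IIEF-15 without any erectile function medical assistance".

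Visit 2 scores are used in three places:

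- Recovery at each time point is "based on whether the IIEF-5 score is larger or equal to 15" (SAP 3.6.1).
- Time to recovery is the "time from surgery to the time of first reaching an IIEF-5 score larger or equal to 15" (SAP 3.6.2). The curve uses visits 2 to 4 and takes every man as not recovered at entry (SAP 4.9.2).
- The not-at-random sensitivity analysis imputes missing 12-month scores by "assuming the IIEF-5 score would have remained similar to the last score observed before dropping out" (SAP 4.11.2).

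The primary analysis (SAP 4.7) uses men with an observed 12-month IIEF-5, and visit 4 opens at 9 months.

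**The concern.** The recall period and the acceptance window do not fit together. A man who completes visit 2 before 3 months and answers the items as worded is describing, in part, the weeks before his operation, when he was required to be potent.

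The recovery definition gives no protection. One score of 15 or more is enough, no confirmation is required, and a later fall does not reverse the event. The curve also assumes that nobody has recovered at the day of surgery, yet an early form asks largely about the time before that day.

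At stake is the early part of two listed outcomes, recovery at 3 months and time to recovery. False events in both arms raise both curves and narrow any true gap between them. Second, a man last seen at an early visit 2 would enter the 4.11.2 imputation with a score that may partly reflect preoperative function. Elsewhere the SAP scores missing information conservatively, and this works in the opposite direction.

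**Working it through.** The documents give no figure for recall overlap, so there is nothing of the plan's own to reproduce. The check is built from its stated windows and thresholds.

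**Inputs.** Recall period 3 months (SAP Appendix 6.1, 6.2). Earliest visit 2 at 1 month (SAP 3.3) or about 1.5 months (Protocol 7.4). Entry score 22-25 (SAP 1.1). Recovery threshold 15 (SAP 3.6.1). Lowest IIEF-5 score 1 (SAP 3.4). Planned dropout 10% (SAP 1.4).

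**Step 1: overlap.** With t months from surgery to the form, preoperative share = max(0, 3 − t) / 3.

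| t (months) | Preoperative months | Share |
|---|---|---|
| 1 | 2.0 | 67% |
| 1.5 | 1.5 | 50% |
| 2 | 1.0 | 33% |
| 3 or later | 0 | 0% |

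Visit 3 opens at 4 months and visit 4 at 9 months, so neither has any overlap.

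**Step 2: can overlap alone produce recovery?** A man who answered only about his preoperative weeks would pass the threshold by at least 22 − 15 = 7 points. A milder assumption is that the reported score is a time-weighted average: share × preoperative score + (1 − share) × postoperative score. For a man with the lowest postoperative score of 1:

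| t (months) | Preoperative 22 | Preoperative 25 |
|---|---|---|
| 1 | (2/3)×22 + (1/3)×1 = 15.0 | (2/3)×25 + (1/3)×1 = 17.0 |
| 1.5 | 0.5×22 + 0.5×1 = 11.5 | 0.5×25 + 0.5×1 = 13.0 |
| 2 | (1/3)×22 + (2/3)×1 = 8.0 | (1/3)×25 + (2/3)×1 = 9.0 |

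At 1 month a man with no function counts as recovered. At 1.5 months he needs a true postoperative score of 8 (from 22) or 5 (from 25), and at 2 months 11.5 or 10. These are below 15, so false recovery remains possible but requires some real function. The entry score comes from the first five IIEF items and the IIEF-5 from items 2, 4, 5, 7 and 15. Using 22-25 as the preoperative IIEF-5 is therefore an approximation.

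**Step 3: effect on the difference in recovery.** If a fraction f of truly unrecovered men is falsely counted in each arm, observed recovery is p + (1 − p)f and the difference between arms is multiplied by (1 − f). For illustration, take a true difference of 14 points. This is borrowed from the sample size section, where it applies at 12 months and a threshold of 21. With f of 5%, 10% and 20% (assumed), the observed difference is 14×0.95 = 13.3, 14×0.90 = 12.6 and 14×0.80 = 11.2 points.

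**Step 4: effect on the 4.11.2 analysis.** Shift in an arm mean = proportion missing × share last seen at visit 2 × share of those forms before 3 months × inflation in points. The 10% is the planned dropout; the other inputs are assumptions.

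- Low: 0.10 × 0.25 × 0.10 × 5 = 0.01
- Middle: 0.10 × 0.33 × 0.30 × 10 = 0.10
- High: 0.10 × 0.50 × 0.30 × 14 = 0.21
- Ceiling, with every dropout last seen at 1 month: 0.10 × 1 × 1 × 14 = 1.4, or with 16 points, 1.6

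The shift has the same sign in both arms. The between-arm difference moves only if form timing, dropout or inflation differs by arm.

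**The case against.** The case for leaving the plan alone is substantial. Collection was aimed at 3 months, and 1 month is only an acceptance limit. Men may well answer about life since the operation whatever the item says. Under time-weighting, only forms near the lower edge of the window reach 15 with no real function. The recovery outcomes are descriptive and untested. The 4.11.2 method is model-based multiple imputation stratified by arm, not simple carry-forward of one man's score. All of this stands, and it limits the point to a minor one.

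The argument that carry-over cancels because it acts in both arms does not fully stand. It is broadly fair for a common shift in means. It fails for a threshold outcome, where the difference shrinks as in step 3.

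The objection to a hard 90-day exclusion is also sound. It would cut at the target visit date. A form from day 85 has only 5/90, about 6%, of its recall before surgery, yet it would be lost. Under 4.11.2, men with no IIEF data at visits 2 to 4 are given the lowest score at visit 2. A dropout whose only form is early could fall under that rule.

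A reader might infer that the primary result is contaminated, especially from Protocol 12.2.5, which plans multiple imputation from all time points. The documents do not support that: SAP 4.7 analyses observed visit 4 scores, whose recall is wholly postoperative. A reader might also infer that about half of visit 2 forms are affected. That would need dates symmetric around 3 months, which the documents do not report, and it would count a form one day early the same as one at 1 month.

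**Conclusion.** The conflict between the recall period and the visit 2 window is in the text and holds. Up to 67% of the recall period can be preoperative under the SAP window, and up to 50% under the protocol's. The consequence is possible false early recovery in the 3-month table and the Kaplan-Meier curve. There is also a small possible effect on the not-at-random sensitivity analysis, 0.01 to 0.21 points per arm mean across the assumed low to high cases.

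The primary analysis, the visit 3 and visit 4 scores and the sample size are untouched. Whether carry-over occurred cannot be judged from the documents, because they give neither the distribution of visit 2 dates nor any evidence of how men read the items. The score illustrations rest on time-weighted answering, and the dilution figures on an assumed f. Severity is minor.

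**What to change.** - **3-month table:** show visit 2 IIEF forms dated before 90 days separately from later ones, by arm. Give the distribution of form dates and the number of forms with imputed dates. SAP 3.3 places a form with no recoverable date at the expected time point, so any overlap in those forms would otherwise go unseen.
- **Recovery curve (SAP 4.9.2) and not-at-random analysis (SAP 4.11.2):** keep both as planned, and repeat each with IIEF forms dated before 90 days set aside.
- **In the 4.11.2 repeat:** treat a man whose only form is early as having a missing visit 2 score, imputed at random. Do not treat him as having no data and so assign him the lowest score.
- **Windows:** reconcile the visit 2 windows in SAP 3.3 and Protocol 7.4.
- **ICIQ:** leave its rule unchanged. The ICIQ items in Appendix 6.3 state no 3-month recall.

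The cost is a few lines of SAP text, a date filter and two repeat analyses. Early estimates in the repeats will be less precise because forms near the target date are set aside.
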